2.0 OBJECTIVES AND SCIENTIFIC AIMS

Primary objective:

- Determine the rate of pathologically negative MRI-guided biopsy after neoadjuvant combination olaparib-pembrolizumab therapy at 12 weeks, in the patient population

Secondary objectives:

- Determine the safety and tolerability of combination olaparib-pembrolizumab therapy in the neoadjuvant setting
- Determine the rate of pathologically negative MRI-guided biopsy after neoadjuvant combination olaparib-pembrolizumab therapy at 12 weeks, in the subpopulation of patients with PD-L1-positive disease
- Evaluate the association of pathologically negative MRI-guided biopsy and imaging complete response on MRI after neoadjuvant combination olaparib-pembrolizumab therapy at 12 weeks, in the patient population
- Evaluate the association of pathologically negative MRI-guided biopsy at 12 weeks and the rate of pathologic complete response at the time of surgery after neoadjuvant combination olaparib-pembrolizumab therapy +/- SOC chemotherapy, in the patient population
- Determine the rate of pathologic complete response after pre-operative treatment including neoadjuvant combination olaparib-pembrolizumab therapy +/- SOC chemotherapy, in the patient population

Exploratory objectives:

- To evaluate changes in tissue expression of selected immune markers at baseline, on-treatment and post-treatment from patients receiving neoadjuvant pembrolizumab/olaparib. Specifically, we will focus on CD3, CD4, CD8 to profile T-cells, CD11b/c, CD163, and CD68 for macrophages.
- To evaluate the potential effects of neoadjuvant pembrolizumab/olaparib on cGAS-STING pathway expression, by comparing tissues obtained at baseline, on-treatment and post-treatment period. Specifically, we will use validated antibodies that have been rigorously profiled in the [name] Laboratory to stain for cGAS and assess its subcellular localization in micronuclei, STING, and ENPP1 – a negative regulator of cGAS-STING signaling.
- To perform high-throughput sequencing of the TCR- β CDR3 region in both tumor specimens and peripheral blood mononuclear cells (PBMCs) using the ImmunoSEQ immune profiling system to describe T-cell repertoire dynamics in patients receiving neoadjuvant pembrolizumab/olaparib.

- To characterize the genomic alterations and evolution of disease during neoadjuvant pembrolizumab/olaparib in patient with germline mutations in DNA damage repair genes.

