13.1 Target Lesions

A baseline and presurgical imaging study of the breast is required as necessary for clinical management; ultrasound, mammogram and MRI may be pursued. The baseline imaging must be obtained within 28 days (+/- 7 days) of beginning therapy. If the participant demonstrates clinical progression at any time, repeat imaging is required. If there is discordance (clinical progression, but radiographic stable disease or response), study PI should be contacted to solve discordance.

In the event of multifocal or multicentric disease in the breast, the investigator must determine which will represent the target lesion. This should remain consistent throughout the study. The target lesion should be selected on the basis of its size (lesion with the longest diameter) and suitability for accurate repetitive measurements (either by imaging techniques or clinically).

Response criteria are based on the RECIST 1.1 criteria:

Imaging Complete Response (CR):	Complete disappearance of the target lesion
Imaging Partial Response (PR):	Greater than or equal to 30% decrease in the longest diameter (LD) of the target lesion taking as reference the baseline LD
Imaging Progressive Disease (PD):	Greater than or equal to 20% increase in the LD of target lesion taking as reference the baseline LD or the appearance of one or more new lesions
Imaging Stable Disease (SD):	Neither sufficient shrinkage to qualify for PR nor sufficient increase to qualify for PD taking as reference the baseline LD

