The primary endpoint is pathologic assessment of MRI biopsy after neoadjuvant combination olaparib-pembrolizumab therapy at 12 weeks. The primary efficacy endpoint will be evaluated following completion of neoadjuvant therapy with combination olaparib and pembrolizumab X 12 weeks. In the primary analysis, patients whose 12-week imaging assessment or biopsy is not available will be counted as failures in the primary endpoint.

Patients are evaluable for the primary efficacy analysis if they have completed the 6-week assessment. An exception to this includes the rare patients who progressed during the first 6 weeks. These patients will be included in the primary analyses as failures. Note that any patients with progression or who drop out of the study from week 6 to 12 will be counted as failures for primary 12 week endpoint. Also note that patients who require a switch to SOC chemotherapy/ pembrolizumab after the 6 weeks biopsy

will be considered failures for the primary endpoint. All patients are evaluable for the safety analyses.

All evaluable patients (groups 1-3) will be included in our primary analysis. The sample size for this study is calculated using a Simon two-stage minimax design comparing a null true imaging-based complete response rate of 50% vs 75%. Our null rate comes from published literature which reports pCR rates in the range of ~44-54% in patients receiving neoadjuvant cytotoxic chemotherapy and ~53-65% in patients receiving either neoadjuvant immunotherapy or a targeted agent like a PARPi^{59, 73, 74,75}. In the first stage, 14 patients will be accrued. If there are 7 or fewer responses, then the study will be stopped. If 8 or more responses are observed, an additional 9 patients will be accrued for a total of 23 patients. If 16 or more responses are observed in 23 patients, the study regimen will be deemed successful. If 15 or fewer responses are observed, the study will be deemed unsuccessful. This design has a one-sided type I error rate of 0.05 and power of 0.80. The probability of stopping the study under the null is 0.60. At the end of the study, the image-guided biopsy CR rate will be calculated with a 95% confidence interval.

Up to 23 evaluable patients will be enrolled on this study. We anticipate enrolling 1-2 patients per month.

Secondary endpoints

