There are several secondary endpoints. First, safety and tolerability of the study regimen will be summarized using frequencies according to the CTCAE Version 5. Common side effects are listed in Section 15.0. The rate of pathologically negative MRI-guided biopsy at 12 weeks will be calculated in the subpopulation of patients with PD-L1-positive disease. In the neoadjuvant setting the rates of PD-L1 positivity were reported in two large prospective trials: Keynote 522 ~80% of patients with TNBC were PD-L1+ and in the NeoTrip trial ~56% of tumors were PD-L1+. In the metastatic setting the numbers have been varied but in the large clinical trials the rate of PD-L1 positivity was ~40%.

Data on MRI-guided biopsies and MRI images will be collected at baseline, at 6 weeks and at 12 weeks following entry into the study. The correlation of response as measured by the MRI - guided biopsy vs MRI images will be evaluated at each timepoint using the McNemar's test for paired samples. The correlation of response as measured by the MRI-guided biopsy collected post-treatment vs pCR at surgery will be evaluated using the McNemar's test for paired samples and the Kappa statistic. The overall pathologic complete response rate will be calculated with a 95% confidence interval.

Analysis of exploratory endpoints

These exploratory analyses will be descriptive/graphical in nature, and are designed to generate new hypotheses to be tested in future clinical studies.

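### McNemar's test, the only analysis planned for biopsy versus MRI response, compares marginal rates and cannot answer the stated association objective

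*Combined protocol and SAP*

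**What the plan says.** The secondary objective in Section 2.0 reads: "Evaluate the association of pathologically negative MRI-guided biopsy and imaging complete response on MRI after neoadjuvant combination olaparib-pembrolizumab therapy at 12 weeks".

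Section 14.0 (Secondary endpoints) describes the same question as a correlation of response and assigns the method: "biopsy vs MRI images will be evaluated at each timepoint using the McNemar's test for paired samples". The timepoints come from the sentence before it: "Data on MRI-guided biopsies and MRI images will be collected at baseline, at 6 weeks and at 12 weeks following entry into the study".

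The following sentence treats the other pairing differently: biopsy against "pCR at surgery will be evaluated using the McNemar's test for paired samples and the Kappa statistic". Kappa is therefore planned for biopsy versus surgical pCR but not for biopsy versus MRI.

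Section 13.1 supplies the binary MRI variable, defining imaging complete response as "Complete disappearance of the target lesion". The ceiling on the number of pairs is in Section 14.0: "Up to 23 evaluable patients will be enrolled on this study".

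**The concern.** The objective asks whether patients with a negative biopsy tend to be the same patients who have an imaging complete response. McNemar's null hypothesis is that the two methods call response at the same overall rate. Those are different questions. Two methods can have equal rates and pick entirely different patients, or pick nearly the same patients while one is consistently stricter.

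Because the plan labels the comparison a correlation, a non-significant result could be misread as agreement and a significant one as lack of correlation. Neither reading is valid. If the plan is followed exactly, a named secondary objective has no analysis that can answer it. An association measure chosen after the table has been seen would be post hoc.

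**Working it through.** **Inputs.** At most 23 pairs (Section 14.0). There may be fewer at week 12, because Section 4.1 repeats the MRI and biopsy only in patients who stay on study therapy beyond 6 weeks. The plan gives no expected imaging complete response rate, no cell counts and no figure for this analysis, so there is no stated result to reproduce. The tables below are assumptions chosen to show the property.

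**Notation.** *a* = both methods call response (biopsy negative and MRI complete response); *b* = biopsy only; *c* = MRI only; *d* = neither; *n* = a + b + c + d.

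**Formulas.**
- Exact McNemar: two-sided binomial test of min(b, c) out of b + c with probability 0.5. Cells *a* and *d* do not enter.
- Kappa = (po - pe)/(1 - pe), with po = (a + d)/n and pe = [(a + b)(a + c) + (c + d)(b + d)]/n².
- Fisher's exact test on the full 2x2 table.

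**Results for n = 23.**

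| a/b/c/d | Pattern | po | pe | Kappa | Fisher p | McNemar p |
|---|---|---|---|---|---|---|
| 12/0/0/11 | perfect agreement | 23/23 = 1.000 | 265/529 = 0.501 | 1.00 | 7 × 10⁻⁷ | 1.0 |
| 6/6/6/5 | unrelated | 11/23 = 0.478 | 265/529 = 0.501 | -0.05 | 1.0 | 1.0 |
| 1/10/10/2 | largely opposed | 3/23 = 0.130 | 265/529 = 0.501 | -0.74 | 0.0006 | 1.0 |
| 10/0/6/7 | clear association, MRI calls response more often | 17/23 = 0.739 | 251/529 = 0.474 | 0.50 | 0.007 | 2 × 0.5⁶ = 0.031 |

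The first three rows run from perfect to reversed association, and the planned test returns the same p-value for each. The only significant McNemar result comes from a positively associated table.

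**Small discordant counts.** With five discordant pairs the smallest possible two-sided exact p is 2 × 0.5⁵ = 0.0625. Five or fewer discordant pairs out of 23 therefore cannot give p < 0.05. Good agreement forces a non-significant result, but a non-significant result does not show good agreement.

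**The pilot in Section 3.6.** That study compared biopsy with surgery, which is a different pairing, but it shows which summaries are informative. Twenty patients, 13 with pCR, one false-negative biopsy and 100% specificity give the table 13/1/0/6, with surgical pCR in the place of MRI. McNemar on one discordant pair gives p = 1.0. Accuracy is 19/20 = 95%. With pe = (14 × 13 + 6 × 7)/400 = 0.56, kappa is (0.95 - 0.56)/0.44 = 0.89. The protocol reports the pilot by NPV, accuracy, sensitivity, PPV and specificity.

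**Baseline.** Section 6.1 requires histologically confirmed, measurable disease of at least 1.5 cm, so before treatment the table is 0/0/0/n. There are no discordant pairs, and kappa is undefined because pe = 1.

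**Other parts of Section 14.0.** The association tests among the exploratory endpoints concern immune markers. The ROC work concerns MRI parameters as predictors of pathologic complete response. Neither covers biopsy versus MRI response.

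**The case against.** The strongest reply concerns weight. This is one of several secondary objectives with at most 23 pairs. No decision rule, error rate or power statement depends on it, and the Simon design and primary analysis are unaffected. The paired data already form the 2x2 table, so kappa could still be calculated at reporting. All of that is correct and limits the impact. It does not give the objective a prespecified analysis.

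McNemar's test also answers a legitimate question: whether MRI calls complete response more or less often than biopsy. That stands, and is a reason to keep the test for that purpose.

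The opposed table (1/10/10/2) is remote in practice. The biopsy immediately follows the MRI and samples the same tumor bed, and Section 3.6 cites 83% MRI accuracy for pCR. The point does not need that table: perfect agreement and no relation already share p = 1.0.

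The plan states no rule for interpreting the p-value, so the misreading is a risk rather than a planned step. Kappa appears in the next sentence, so its absence here may be a drafting gap. The baseline test would mislead few readers and is mainly a wording fault. Finally, week 6 lies outside the stated objective, and sensitivity and specificity against biopsy use a reference other than surgical pathology, which the protocol names as its standard. That argues for clear labelling, not for leaving the analysis as it is.

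**Conclusion.** The concern holds for biopsy versus MRI. Applied exactly as written, the plan cannot answer its association objective: the same p-value of 1.0 is compatible with kappa of 1.00, -0.05 or -0.74, and p = 0.031 can accompany real positive association (kappa 0.50). The illustrative cell counts are assumptions, but the conclusion follows from the test's construction and does not depend on them. It does not extend to biopsy versus surgical pCR, where kappa is also planned. The consequence is limited to one secondary objective with at most 23 pairs, and the primary endpoint and sample size are unaffected.

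**What to change.** Replace the biopsy-versus-MRI sentence in Section 14.0 with the following analysis:

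- At weeks 6 and 12, cross-tabulate biopsy (negative or positive) by MRI (complete response yes or no, as defined in Section 13.1). Name week 12 as the analysis that serves the Section 2.0 objective and week 6 as supportive.
- Report Fisher's exact test with the odds ratio for association, and kappa with a 95% confidence interval for agreement.
- Report sensitivity, specificity, PPV and NPV of MRI with exact confidence intervals, labelled as relative to biopsy and not to surgical pathology.
- Keep McNemar's test only as a test of systematic difference between the two response rates.
- Drop the baseline comparison.

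If a shorter text is preferred, the minimum is the week-12 table with kappa and its interval, plus one association measure. The change costs SAP wording and a few lines of code. It needs no new data, patients or procedures.

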- To assess whether early circulating tumor DNA response can predict pathologic response
- To evaluate the potential effects of neoadjuvant pembrolizumab/olaparib on malignant and immune cell diversity, by comparing baseline, on-treatment and post-treatment tissues analyzed with ultra-high resolution single cell genomics and transcriptomics techniques.
- To evaluate a novel Echo-planar imaging (EPI) based Magnetic Resonance Fingerprinting (MRF) sequence for rapid measurements of quantitative susceptibility mapping, proton Density (PD), T1 and T2 relaxation maps, which would enable quantitative evaluation of the tumor over time and determine the ability of these parameters to predict breast cancer pathologic response.
- To evaluate a novel Chemical exchange saturation transfer Magnetic Resonance Fingerprinting (CEST-MRF) sequence, which is a multiparametric molecular imaging method for rapid simultaneous measurement of the water T1 and T2 relaxation maps, the pH-dependent amide exchange rate and volume fraction and the macromolecular exchange rate and volume fraction, and determine the ability of these parameters to predict breast cancer pathologic response.

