When parameters of immune response are measured (including TILS, multiplex IH and cGAS-STING pathway expression) continuous variables will be summarized with means and standard deviations. Dichotomous and categorical variables will be summarized using proportions with exact 95% confidence intervals and counts, respectively. These summaries will be computed for each treated patient at multiple time points, including before treatment, during and after pembro/olaparib administration, as indicated in the study schema. Plots will be used to show the changes in immune response over time for each individual. For each patient, comparisons in the pre and post-treatment responses will be compared using paired t-tests (or Wilcoxon signed rank tests if appropriate) for continuous variables and McNemar's test for dichotomous or categorical variables. Associations between immune responses will be explored graphically (e.g. scatterplots, boxplots) and numerically (e.g. associations, χ^2 tests). Associations between early ctDNA values and pathologic response will be evaluated descriptively and graphically.

Bioinformatic and biostatistical analysis of differentially expanded/contracted clones in PBMC and tumor tissue after 6 and 12 weeks of treatment will be performed using Fisher's exact test with multiple testing correction by Benjamini-Hochberg procedure which controls false discovery rate (FDR < 0.05). Differential clonotypes will be further analyzed for tissue and longitudinal PBMC representation in pCR and non-pCR patients.

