Analysis of the EPI-MRF and CEST-MRF: Maps from these sequences will be correlated with the histopathology measures. We will evaluate changes pre, 6-week and 12-week post neoadjuvant chemotherapy. We will compare these parameters between patients with a pathologic complete response versus those with no-pathologic complete response using two sample t-tests, or Wilcoxon rank sum tests if data are highly skewed. Once significant parameter changes are identified by these tests, we will then run ROC/AUC analyses to identify optimal cut-points by maximizing the Youden index (i.e., sensitivity + specificity - 1). Depending on specific requirements we may consider assigning various weights to sensitivity and specificity as well. Predictive power quantified by AUC can also be compared across different imaging parameters (e.g., T1-weighted, diffusion and DCE scans) and statistical significance level will be derived by, e.g., the Delong-Delong test to compare the predictive power of both EPI-MRF and CEST-MRF to the standard protocol. For time-to-event type endpoints, we will apply the Cox proportional hazards regression model (endpoints will be landmarked to ensure they are baseline factors in the Cox model) to identify significant factors and compute the concordance index for their predictive power. We will also try to identify optimal cut-points using the maximal chi-square method. Graphical presentation of the parameter measurements will be examined for patterns and appropriate longitudinal analysis tools may be used if such analyses are deemed necessary.

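### The MRF imaging parameters are screened for significance and then given AUCs and Youden cut-points in the same patients (at most 23), so any useless parameter that passes the screen will look predictive

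*Combined protocol and SAP*

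**What the plan says.** Section 2.0 lists two exploratory imaging objectives, one for each MRF sequence. Both aim to "determine the ability of these parameters to predict breast cancer pathologic response".

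Section 14.0, in the paragraph on EPI-MRF and CEST-MRF, sets the analysis. Parameters and their changes are compared between pCR and non-pCR patients by two-sample t-test, or by Wilcoxon rank sum test if the data are skewed. Then: "Once significant parameter changes are identified by these tests, we will then run ROC/AUC analyses to identify optimal cut-points by maximizing the Youden index". The paragraph also allows sensitivity and specificity to be weighted, AUCs to be compared with the standard protocol (DeLong is given as an example), and a further cut-point search by the maximal chi-square method.

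The paragraph states no significance threshold, number of tests, multiplicity control, resampling or validation set. Under the same exploratory heading, the T-cell clone analysis does carry "multiple testing correction by Benjamini-Hochberg procedure". That heading opens by describing all the exploratory analyses as descriptive and hypothesis-generating.

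On sample size: "Up to 23 evaluable patients will be enrolled on this study".

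**The concern.** A parameter reaches the ROC step only because it already separated the two outcome groups in these patients. Its AUC in the same patients is therefore biased upward, and choosing the cut-point that maximises the Youden index adds further optimism. In about 23 patients both effects are large.

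The stated objective is to determine predictive ability, and this procedure overstates that quantity for any parameter selected by chance. The exploratory label limits how the result may be used, but it does not make the estimate less biased. A later imaging study planned around a reported AUC or cut-point would inherit the error.

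**Working it through.** **1. Sample size.** The plan gives no figure for the MRF analysis itself, so I checked the design that fixes the available sample: 14 then 23 patients, continue with 8 or more responses, success with 16 or more, 50% against 75%.

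- Early stopping under the null: P(X ≤ 7 | n = 14, p = 0.5) = 0.5 + C(14,7)/2^15 = 0.5 + 3432/32768 = 0.6047. The plan says: "The probability of stopping the study under the null is 0.60".
- The exact two-stage calculation gives type I error 0.0462 and power 0.8016. The plan says: "This design has a one-sided type I error rate of 0.05 and power of 0.80".

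The design reproduces. For the MRF analysis 23 is an upper limit. Week-12 MRI covers only patients who stay on the combination beyond week 6 (Section 4.1), and the sequences are implemented on 3T scanners (Section 4.2) although 1.5T units are also allowed (Section 11.0).

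**2. Number of tests (assumption).** Section 2.0 names 4 EPI-MRF parameters (susceptibility, proton density, T1, T2) and 6 CEST-MRF parameters (water T1 and T2, amide rate and fraction, macromolecular rate and fraction), 10 in all. One contrast each gives 10 tests, changes at 6 and 12 weeks give 20, and three time points or contrasts give 30.

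**3. Chance that at least one useless parameter passes, assuming a two-sided 0.05 screen.** With independent tests this is 1 − 0.95^k. With correlated tests it was simulated (2,000 trials per setting, normal data, n = 23, common correlation, all parameters null).

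| Tests (k) | Independent | Correlation 0.3 | Correlation 0.5 | Correlation 0.8 |
|---|---|---|---|---|
| 10 | 1 − 0.95^10 = 40% | 35–37% | 29–30% | 16–19% |
| 20 | 1 − 0.95^20 = 64% | 53–55% | 44% | 24–26% |
| 30 | 1 − 0.95^30 = 79% | 67–68% | 52–53% | 29% |

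Repeat simulations differ by up to about 3 percentage points. The expected number of false passes is 0.05k, that is 0.5, 1.0 and 1.5.

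**4. What a useless parameter shows once it has passed.** The plan does not predict the pCR split. The two splits below correspond roughly to the design's 50% and 75% rates (0.5 × 23 = 11.5; 0.75 × 23 = 17.25).

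| pCR / non-pCR | Mean apparent AUC (truth 0.50) | Mean Youden index (truth 0) | DeLong rejection (nominal 5%) |
|---|---|---|---|
| 12 / 11 | 0.77–0.78 | 0.54–0.55 | 8–12% |
| 17 / 6 | 0.81 | 0.61–0.62 | 11–17% |

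The AUC and Youden columns hardly change with the number of tests or their correlation. The DeLong column compares the best selected parameter with an equally useless standard parameter, in trials where something was selected. The AUC excess is 0.77 − 0.50 = 0.27 to 0.81 − 0.50 = 0.31. A useless parameter that was not selected already shows a Youden index of 0.33 (12/11 split) from the cut-point search alone. If the trial stops at 14 patients (7/7, 20 tests), the apparent AUC of a selected null parameter is about 0.85.

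**5. What the remedies achieve.**

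- Benjamini-Hochberg at 5% across the MRF tests brings the chance of any false pass down to about 3–6% in every setting tried.
- Bootstrap optimism correction with selection repeated in each resample lowers the best-of-20 null AUC from 0.76 to about 0.60. It removes 0.16 of an excess of 0.26.
- Leave-one-out AUC with selection repeated in each fold gave a mean of 0.41 with SD 0.25 under the null (300 runs). It is biased below 0.50 and too noisy to use.

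**The case against.** A reader might infer that useless parameters will probably be reported as predictive. The documents do not support that.

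- The plan says only that changes must be significant, so 0.05 and the test count are assumptions.
- A given null parameter passes about 5% of the time. At least one passing is more likely than not only with 20 to 30 tests at low correlation, or about 30 tests at correlation 0.5.
- Substantial correlation is plausible, because both sequences measure T1 and T2 and the two changes share a baseline.
- The all-null case is a worst case. Section 3.6 reports that early falls in T1, T2 and proton density predicted response to neoadjuvant chemotherapy.

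A reader might also infer that the DeLong comparison is worthless. It is optional in the text and not expressly confined to screened parameters, and its error is inflated only to about 8–17%.

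The T-cell clone contrast has limits too. High-throughput clonotype screening is a different problem from ten named imaging parameters, so using false-discovery control there and not here is not a contradiction. It does show that the plan accepts error control within exploratory work.

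Finally, Section 14.0 already calls these analyses hypothesis-generating, and no stopping rule, treatment decision, primary endpoint or secondary endpoint depends on them. That stands and keeps the severity low. It does not answer the bias in AUCs and cut-points reported for screened parameters.

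**Conclusion.** The concern holds in a limited form. As written, the rule gives upward-biased AUCs and Youden indices for the parameters it selects. A null parameter that passes shows an AUC of about 0.77–0.81 and a Youden index of about 0.54–0.62. How often this happens is uncertain: with 10 to 30 tests, about 40–79% of trials if the tests are independent, 30–53% at correlation 0.5 and 16–29% at correlation 0.8.

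These figures assume a two-sided 0.05 t-test screen, normal data, 23 evaluable patients, splits of 12/11 or 17/6, and no real signal in any parameter. The inflation after selection is robust to the test count and correlation, but the selection probability is not.

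**What to change.** Amend the MRF paragraph of Section 14.0 before outcome data are examined:

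- State the list of parameter-by-time tests and the screening threshold.
- Report AUC with a confidence interval for every MRF parameter and time point, not only the significant ones.
- Apply Benjamini-Hochberg across the MRF tests, as the section already does for T-cell clones.
- Give bootstrap optimism-corrected AUC and Youden index, with selection and cut-point search repeated in each resample. State that the correction is only partial at this sample size, and do not rely on leave-one-out AUC.
- Label all cut-points as unvalidated.
- Report DeLong comparisons descriptively for any parameter chosen by the screen.

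The cost is protocol text and analysis code, with no extra patients, scans or visits. The downside is less favourable AUCs and fewer parameters flagged, including possibly some with real but moderate value. Reporting every parameter's AUC limits that loss.
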